#### **4. Study population**

Study counselors will enroll consecutive eligible, consenting pregnant adolescent girls ( $\geq 16$  years) and women in ANC (n=600 women per site; N=1200 pregnant women) and follow them up for 12-months postpartum or until censorship for a mean of 18-months' follow-up.

##### Inclusion Criteria:

- 1.  $\geq 16$  years old**
- 2. confirmed HIV-negative (confirmed with a 4th generation antigen HIV test)**,
- 3. Intend on giving birth in the MOU facility**
- 4. confirmed to be pregnant**
- 5. without psychiatric or medical contraindications to PrEP.**

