### **1. Determine the distribution of women across the PrEP cascade:**

- (1) Evaluate the proportion of pregnant and breastfeeding women who initiate PrEP out of all women offered PrEP**
- (2) Evaluate the proportion of pregnant and breastfeeding women who are retained in the PrEP cohort**
- (3) Evaluate the proportion of pregnant and breastfeeding women who initiate PrEP who adhere to PrEP using objective dried blood spot measures and subjective measures of self-reported pill count and adherence**
- (4) Evaluate the proportion of pregnant and breastfeeding women on PrEP (and not on PrEP) who acquire HIV, who transmit HIV to their infant, and who report adverse events**

- 2. Evaluate patient and provider-level factors associated with the PrEP cascade using quantitative and qualitative approaches (including in-depth interviews)**
- 3. Apply an established mathematical model to simulate the impact of improvement in the PrEP cascade on HIV infections averted (maternal and perinatal)**
- 4. Evaluate the effect of PrEP on vaginal microbiome in pregnant women and the consequent relationship to adverse pregnancy outcomes.**

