**Step 5: Screening and study consent process:** If the client agrees to participate in the study (*she does not have to agree to take PrEP*), she will be referred to the study recruiter on site where the study counselor will review the **screening consent form** to evaluate study eligibility (see study inclusion, exclusion criteria). Following affirmative answers on the screening consent form the counselor will conduct a rapid HIV test, to test for acute HIV infection using an antigen/antibody test, and a Hepatitis B surface antigen test. Women who test positive for HIV (antigen, antibody or both) and/or Hepatitis B are ineligible for the study and will be referred to the clinic nurse for treatment and care.

All participants who are eligible for the study and agree to participate in the study will receive the study consent form and listen to/watch the consent form on a previously recorded video in Xhosa to ensure that she understands the study design and consent form before signing, asking questions to ensure comprehension.

**Hepatitis B infection (all women at screening):** The blood draw will also be used to test for active Hepatitis B infection using Hepatitis B surface antigen (HBsAg). Women who test HBsAg+ will be excluded from the study and referred for care according to national protocol

- **In addition, we will draw 1ml of serum to be frozen for testing in the case of discrepant results between the Determine HBsAg+ and NHLS laboratory results.**

**Infant consent form:** The participant will review and sign the infant consent form when she returns for her first post-partum visit with her infant.

**Step 6:** Participants will self-collect two vaginal swabs for storage: (1) for laboratory STI testing and (2) for vaginal microbiome analysis. Results for STI testing will be provided in 2-3 weeks after analysis and participants will be called in with STI+ results for treatment and partner referrals

**Step 7:** All participants will complete the baseline survey, which may take approximately 30-45 minutes to complete.

**Step 8:** The participant will receive individual counseling about HIV prevention in pregnancy including PrEP. Risk reduction counseling will be provided for all women and will include:

- **Consistent and correct use of condoms**
- **Knowing your status and partner's status**
- **If partner is HIV infected, should be on ART and achieve viral suppression**
- **Use of drugs and alcohol increases risk of HIV**

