**Step 9: For all participants who decide to take PrEP, the study nurse will draw blood to test for baseline creatinine tests**

- Women with low creatinine can participate in the study but can only receive PrEP if their eGFR >60mL/min
- Test results will be received in 24-48 hours. If eGFR <60mL/min then the nurses will call participant to return and immediately stop using PrEP until they have a normal creatinine result (can return in following month)

**Step 10:** Participants who opt to take PrEP will receive counselling on the risks and benefits of PrEP. Following the counseling they will be asked: “Do you want to start taking PrEP today to prevent HIV? You will need to take it daily for it to be effective.” Her response will be recorded.

If yes:

1. The nurse will provide the participant with a 1-month supply of TDF-FTC and invite her to return in 1 month for her next study visit (after then they will receive 3 months prescriptions to correspond with their quarterly PrEP-PP study visit).
2. Nurses will provide contact information to the participant and ask her to call to report any side effects or adverse events while on PrEP, and nurse will track and report serious adverse events to study PIs, Pediatrician, and Obstetrician to decide on how to treat women and infants who have adverse events.

If she says she does not want to start PrEP, woman will be in the deferred PrEP arm:

1. The nurse will schedule her to return in 3 months for the follow-up study visit

**Step 10:** Participants will receive study staff contact information, instructions to call with any questions, and will be scheduled for their next visit in 1 month if on PrEP, or 3 months if not on PrEP, for the next study visit

**Step 11:** The study counselor will provide the mother with an appointment card and invitation for her partner to return to receive couples' HIV testing and counseling (if in a relationship). The session will end by encouraging the client to implement her/his risk-reduction plan (including PrEP if applicable and consistent condom use, couples testing) to prevent HIV acquisition.

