## **Laboratory tests in all women in the cohort:**

- **STI testing:** Self-collected vaginal swab kits will be provided to all participants along with an explanation for their use. Swabs will be analyzed in the laboratory for chlamydia and gonorrhea. Results for STI testing will be provided in 2-3 weeks after analysis and participants will be called in with STI+ results for treatment and partner referrals
- **HIV testing.** As part of the standard of care, all pregnant and breastfeeding women will be tested for HIV using serial rapid HIV tests at each antenatal and postnatal care visit. In addition, PrEP-PP study staff will test for HIV using antigen and antibody HIV tests to rule out acute HIV infections.
  - **Seroconversion.** If a woman, infant or partner seroconverts at any point during the study (including antigen+, antibody+ or antibody/antigen+), they will stop PrEP immediately and be referred to the clinician on duty to initiate ART on the same day, following counseling about PMTCT, breastfeeding, disclosure, and ART adherence, per the SA National Protocols [17]. Seroconverted women will be censored from the remainder of the study and referred to the clinic to initiate ART.
  - If a woman seroconverts while on PrEP, there may be a risk of ART resistance, though research has demonstrated that the risk of ART resistance is very low [12, 13]. In the case of seroconversion, Drs [name] and [name] will follow seroconverters with the study team to evaluate if the patient achieves viral suppression within 6 months of ART start, and if not, she will be referred for specialist attention for testing for ART resistance and clinical follow-up.

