**Table 1. Study measures for PrEP-PP for AIM 1**

Primary Outcomes	Measurement	Source	Frequency
PrEP initiation	# of women who initiate PrEP over time / total # of women in active cohort = proportion of women who initiate PrEP	Electronic provider log (REDCap)	Quarterly
PrEP continuation	# of women on PrEP who return for study visits (do not miss more than 1 visit) / total # of women in active cohort who are prescribed PrEP= proportion of women on PrEP who continue in PrEP study	Electronic provider log (REDCap)	Quarterly
PrEP persistence (subjective)	# of women reporting taking PrEP in $\geq 5$ out of last 7 days or $\geq 25$ out of last 30 days (self-reported)/ total woman-time on PrEP in active cohort = PrEP persistence rate (subjective)	Electronic provider log (REDCap)	Quarterly
PrEP persistence (objective)	# of women taking PrEP who have $\geq 600$ fmol/punch (~7 doses/week) from DBS TDF-DP at 3rd trimester, delivery, and 6 weeks postpartum (and during sexual risk periods during that time) / total woman-time on PrEP in active cohort = PrEP persistence rate (objective)	Lab analysis of TDF-DP measures	Yearly and end of study
Secondary Outcomes			
Prevention effective persistence	4. # of women reporting adherence to PrEP (as per PrEP persistence subjective measure)/ total woman-time reporting sexual activity in past 30 days	Electronic provider log (REDCap)	Quarterly
	5. # of women having TDF-DP in DBS (as per PrEP persistence objective measure)/ total woman-time reporting sexual activity in past 30 days	Lab analysis of TDF-DP measures	Yearly and end of study

Prevention effective continuation	# of women who don't miss any PrEP study visits/ total woman time reporting sexual activity in prior visit	Electronic provider log (REDCap)	Quarterly
Predictors of attrition at key steps in the PrEP cascade	Individual, pill/study and disease specific predictors of PrEP initiation, continuation and persistence	Study CRFs and in-depth interviews (month 7 and12) (mixed methods)	End of study
Healthcare provider attitudes and knowledge about PrEP in pregnancy	Provider knowledge about PrEP and barriers/facilitators to PrEP prescription in ante and postnatal care	In-depth interviews	Year 1 of study
HIV outcomes	HIV testing data: HIV-uninfected, HIV incidence in mother and child (if mother seroconverts) compared by PrEP use/non-use	Electronic provider log (REDCap)	End of study

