- iii. **Disease-specific factors:** Collected from CRFs (in all participants, not just those who decide to take PrEP) on partner's HIV status (including knowledge of serostatus and uptake of couples testing and counseling), perceived risk of HIV exposure and acquisition, perceptions of PrEP efficacy, and stigma associated with PrEP and HIV. Collected from the sub-set of women participating in the IDIs.
- b. **HIV outcomes:** Describe the frequency of HIV outcomes, including maternal and infant incident HIV. Analyses will include pure-count and person-time approaches. While we expect the frequency of adverse HIV-related outcomes to be low, we will describe characteristics of women who did/did not acquire HIV, and consider further analyses using the approaches outlined.

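### Infections acquired just before a PrEP start but not yet detectable would by default count as HIV in PrEP users; the SAP needs a pre-specified listing and a sensitivity analysis

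*Combined protocol and SAP*

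**What the plan says.** Protocol section 4 (Inclusion Criteria) requires women to be "confirmed HIV-negative (confirmed with a 4th generation antigen HIV test". At enrolment (section 5, Step 5) "the counselor will conduct a rapid HIV test, to test for acute HIV infection using an antigen/antibody test". In Step 10 a woman who accepts is asked whether she wants to begin that day, and "The nurse will provide the participant with a 1-month supply of TDF-FTC and invite her to return in 1 month". Creatinine results follow one to two days later, with a recall if abnormal, so dispensing is clearly same-day. A woman who declines returns at 3 months. Women not on PrEP are asked again at each follow-up visit, and restarts are allowed.

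Under Laboratory tests in all women, "all pregnant and breastfeeding women will be tested for HIV using serial rapid HIV tests at each antenatal and postnatal care visit", and study staff also "test for HIV using antigen and antibody HIV tests to rule out acute HIV infections". Section 5 promises an HIV test at every study visit. No HIV RNA test is named, and the frozen screening serum is reserved for discrepant hepatitis B results.

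Protocol objective 1(4) is to "Evaluate the proportion of pregnant and breastfeeding women on PrEP (and not on PrEP) who acquire HIV". The SAP's Table 1 of study measures lists, as a secondary outcome, "HIV incidence in mother and child (if mother seroconverts) compared by PrEP use/non-use". SAP 2.5, item b, says: "Describe the frequency of HIV outcomes, including maternal and infant incident HIV", with counts and person-time. The adverse-event template in SAP section 4 sets antibody, antigen and combined positives side by side for users and non-users, with use meaning PrEP taken in the last 30 days.

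**The concern.** An antigen/antibody test cannot detect an infection in its first days. A woman infected shortly before enrolment can test negative, leave with PrEP and test positive at her next visit. Under the 30-day definition she is then a user, although PrEP could not have prevented that infection. Each later start or restart creates the same situation and moves an infection acquired off PrEP into the user column.

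If PrEP protects, this raises the users' rate and pulls the comparison toward no effect. The plan expects few HIV events, so even a handful of misplaced ones could be read as failures of PrEP. A rule written after the seroconversions are known would look selective.

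**Working it through.** **Inputs from the documents.** Enrolment 1,200 and 60% initiation (protocol section 6; SAP 2.2). Background incidence *I* = 10.7 per 100 person-years and rate ratio in women *RR* = 0.57, 95% CI 0.34 to 0.94 (protocol section 1). Mean follow-up 18 months.

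**Assumptions, not in the documents.** Undetectable window *w* = 14 to 28 days, that is 14/365 = 0.0384 to 28/365 = 0.0767 years. Mean time on PrEP *T* = 0.9 to 1.1 years, varied below to 0.5 and 1.5. A lower incidence of 2 per 100 person-years. Incidence constant over time.

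**Step 1, the plan's own figure.** 1,200 × 0.60 = 720 initiators, as SAP 2.2 states. The plan gives no expected HIV count by PrEP status and no test window.

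**Step 2, undetected at start = 720 × I × w.**
- At 10.7 per 100: 720 × 0.107 × 0.0384 = 3.0; with 0.0767, 5.9.
- At 2 per 100: 0.6 to 1.1.
- The 480 women who never start pass the same screen: 480 × 0.107 × w = 2.0 to 3.9.

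**Step 3, net effect on rates.** Infections that become detectable during on-PrEP time *T* are those acquired from *w* before the start to *w* before the end. The apparent ratio is [w + RR(T − w)]/T = RR + (w/T)(1 − RR), and net inflation is (w/T)(1/RR − 1). Among women who never start, early gains and late losses cancel, so their rate is unchanged. The percentages do not depend on *I*.
- Low end: (0.0384/1.1) × 0.754 = 2.6%; ratio 0.585.
- High end: (0.0767/0.9) × 0.754 = 6.4%; ratio 0.607.
- Net excess events at 10.7 per 100: 720 × 0.107 × w × (1 − 0.57) = 1.3 to 2.5. Expected true on-PrEP infections are 720 × T × 0.107 × 0.57 = 40 (T = 0.9) to 48 (T = 1.1).

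**Step 4, sensitivity (w = 14 to 28 days): net inflation, then apparent ratio.**

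| True ratio | T = 0.5 y | T = 0.9–1.1 y | T = 1.5 y |
|---|---|---|---|
| 0.34 | 15–30%; 0.39–0.44 | 7–17%; 0.36–0.40 | 5–10%; 0.36–0.37 |
| 0.57 | 6–12%; 0.60–0.64 | 3–6%; 0.58–0.61 | 2–4%; 0.58–0.59 |
| 0.94 | 0.5–1.0%; 0.94–0.95 | 0.2–0.5%; 0.94–0.95 | 0.2–0.3%; 0.94 |

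**Step 5, where it concentrates.** For a first retest on day *d*, the share of positives acquired before the start is w/[w + RR(d − w)]. With RR = 0.57:
- d = 30: 14/(14 + 0.57 × 16) = 61%; at w = 28, 28/(28 + 0.57 × 2) = 96%.
- d = 42: 14/(14 + 0.57 × 28) = 47%.
- d = 90: 14/(14 + 0.57 × 76) = 24%; at w = 28, 28/(28 + 0.57 × 62) = 44%.

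**The case against.** The strongest case against is that the effect is small and the outcome minor. HIV is secondary and mainly descriptive, with no HIV model or test specified beyond a comparison by use. A shift of 0.02 to 0.04 is slight beside a confidence interval of 0.34 to 0.94. Women choose PrEP themselves, so confounding is a more obvious threat. This stands, and it limits the weight of the point.

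Two partial safeguards exist. A routine rapid test precedes the study test, but recruitment is at the first antenatal visit and proceeds directly to screening, so it does not close the window. The template separates antigen from antibody positives, which may reveal some early infections but does not date them.

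A simple exclusion rule can also err the other way. By Step 5, at a 14-day window, 39% of positives on day 30 and 53% on day 42 were acquired after the start; removing them would flatter PrEP. A short fixed cut-off may also catch nothing. The protocol tests at every study visit, yet the monthly report template has HIV rows only for baseline and visit 2 onward, none for the refill visit. Both arguments stand and shape the fix.

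A reader might infer a much larger bias by counting every infection undetected at start: w/(RR × T) gives 6 to 15% at 0.57. That figure is gross. It omits infections acquired late in PrEP time and detected afterwards or never.

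**Conclusion.** The gap is real. As written, the plan puts infections already present at a start or restart into the PrEP-user count, because the 30-day definition applies and no rule says otherwise. This is a default arising from silence; no passage states that such infections are attributed to PrEP failure.

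The size is modest: about 3 to 6 affected starters at 10.7 per 100 person-years, and net inflation of about 3 to 6% at a ratio of 0.57. This rests on the assumed window, the assumed time on PrEP and constant incidence. It would be larger with short use or stronger protection, and the distortion is greatest at the first test after a start.

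A reader might also infer that the Aim 3 projections are compromised. The documents do not support that. Aim 3 takes initiation, retention and adherence from the cohort and describes PrEP efficacy as a model assumption; its general wording on parameterising and validating does not say that the user/non-user HIV ratio is an input. The primary cascade outcomes do not depend on this classification. The case for acting is that objective 1(4) asks for HIV acquisition on and off PrEP, and the remedy is cheap if written before the results are known.

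**What to change.** Amend SAP 2.5, item b, and the adverse-event template. Dispensing and the testing schedule are untouched.

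1. State which visit provides the first HIV test after enrolment and after a start or restart, reconciling the protocol with the monthly report template.
2. List every positive at that first test separately as *possibly infected before start*, with the interval from the last negative test and from the start.
3. Keep the planned incidence by PrEP use.
4. Add a pre-specified sensitivity analysis that excludes these events and the matching initial person-time, with one stated lag applied equally to users and non-users. For later starts and restarts, show the events alternatively under the preceding off-PrEP time.
5. State that the rule may also remove true early on-PrEP infections, so both estimates are reported.

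The cost is slightly fewer events and less person-time in the sensitivity estimate. For example, a 28-day lag after enrolment removes 1,200 × 28/365 = 92 of 1,200 × 1.5 = 1,800 person-years (5%); lags after later starts would add to this. A lag shorter than the non-users' 3-month return also requires linking their routine antenatal HIV tests, so the work goes a little beyond SAP wording.

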##### Exclusion criteria:

Individuals not meeting the above criteria or meeting any of the following criteria will be excluded:

- Concurrent enrolment in another HIV-1 vaccine or prevention trial**
- Medical hospitalization in the past year, for reasons not associated with obstetric health (e.g. c-section, miscarriage, pre-eclampsia)**
- Active TB or receipt of TB treatment within the past 30 days**
- History of renal disease**
- Current clinical diagnosis of hypertension**
- Exhibiting psychotic symptoms (including hallucinations, suicidal or homicidal ideations, or violent behaviour)**
- Currently or history of taking an anti-psychotic medication (such as for treatment of bipolar disorder, schizophrenia, or postpartum psychosis following a previous pregnancy)**
- Positive Hepatitis B surface antigen (HBsAg) test on screening**
- History of bone fracture not related to trauma**

- Any other medical, psychiatric or social condition which in the opinion of the investigators would affect the ability to consent and/or participate in the study.

Study censorship will include:

1. Seroconversion
2. Moves away
3. Transfers out of care
4. Lost to follow up (e.g. does not return for study or clinical visit for >8 weeks and study staff are unable to track the participant, or she does not want to continue in the study).

Eligible, consenting women will receive up to R250 in grocery vouchers, transportation and refreshments per visit for their time and effort in the study as well as transportation to the facility. All participants will also receive minor refreshments (e.g. sandwich and cool drink) on the day of their visit.

Procedures for the informed consent process are outlined below. Throughout, trained study staff will ensure that women are aware of their right to refuse and/or withdraw from the study at any time. In addition, study staff will emphasize that all study activities are entirely separate from routine ANC and postnatal care services received and that refusal or withdrawal from the study will have no impact on their ability to access any services provided at any public-sector health facility.

Inclusion of adolescent girls (16+ years old): Our study proposes to enroll pregnant adolescents 16 and 17 years old who will provide unassisted consent. The specific age range covers a critical period of risk of HIV acquisition. Further, *pregnant* adolescent girls are practicing condomless sex and are at elevated risk of HIV acquisition and mother to child transmission. Because of the high HIV incidence and existing policy supporting PrEP among adolescent girls, it would be unethical to not provide adolescent girls and young women with PrEP that might prevent them from acquiring HIV [18].

- All 16 and 17-year-old girls will provide unassisted consent if she chooses to participate.
- We will verify age on participant medical record and/or other official documents (eg, ID book)
- We will not have an upper age limit exclusion criterion for the study

Our definition of unassisted consent meets the following HREC conditions including:

- **The study is no more than minimal risk; and**
- **The nature of the research is acceptable to the Committee, parents or legal guardians or the community at large.**
  - **Our study was approved by the HREC and adolescent girl and young women PrEP is actively being rolled out in South Africa. In particular, we note that HREC has approved projects to use PrEP in adolescent girls ages 16-17 without parental consent in this area (see HREC REF: 567/2016).**
- **Justification for why adolescents are needed in the study:**
  - **Adolescent girls have high HIV incidence and pregnancy rates in South Africa. Girls 16-17 years old are at a critical period of risk of HIV acquisition. Because of the high**

**HIV incidence and existing policy supporting PrEP among adolescent girls, it would be unethical to not provide adolescent girls and young women with PrEP that might prevent them from acquiring HIV**

- **Justification for why adolescents should consent unassisted.**
  - Our formative research has demonstrated that adolescent girls do not attend antenatal care with their parent/guardian and may find it difficult to get parental consent. Further, our study will include sensitive surveys on sexual behaviours which the adolescent may not want to share with their parents or guardians.

Based on our work in this setting, we anticipate that young women ages 16-17 comprised <5% of all HIV-negative pregnant women at the Gugulethu MOU, and in turn we anticipate that this population will comprise <5% of our study cohort.

